The antimuscarinic (anticholinergic) effects of belladonna alkaloid are dose dependent and include relaxation of smooth muscle, bronchodilation, pupil dilation, decreased gastric motility, transient tachycardia, and, most significant for this study, decreased tone and amplitude of ureteral and bladder contractions. B&O suppositories pair the belladonna anti-spasmodic with analgesia of an opioid to minimize discomfort associated with ureteral spasm. B&O suppositories have been used safely in robot assisted laparoscopic prostatectomy studies [15]. Administration of B&O suppositories prior to urologic procedures has been shown to decrease IV pain medication requirements and overall pain postoperatively [14]. The common B&O suppository formulation contains 16.2mg Bella Donna and 30 or 60 mg of opium and may be dosed as 1 suppository 1-4 times a day. The cost of this medication is approximately \$400 for 12 tabs.

Contraindications to this medication include hypersensitivity to belladonna, opiate, or any component of the formulation; glaucoma; severe renal or hepatic disease; bronchial asthma; respiratory depression; convulsive disorders; acute alcoholism; premature labor. Adverse reactions occur with an undefined frequency but may include palpitations, dizziness, drowsiness, pruritus, urticarial, constipation, nausea/vomiting, xerostomia, urinary retention, blurred vision, photophobia. The anti-cholinergic effect of BoNT, when therapy administration is closely monitored, is not likely since a single B&O dose will have worn off long before the 2-4 week onset period of BoNT is complete. Minimal systemic effect has been noted with suppository administration. Additionally, patients undergoing this therapy have theoretically already withstood an anticholinergic trial as a first line treatment for OAB/NB [28, 29].

Study Rationale

Data are lacking to demonstrate the ideal pain control regimen during office injections of BoNT. This is likely due to the relatively new application of this procedure in office. One study comparing average pain during intravesicle injections with use of alkalized lidocaine vs lidocaine gel demonstrated no result [13]. Additionally, it is difficult to accurately represent the patient pain experience. The Numeric Rating Scale (NRS) is a

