Potential confounding factors will be considered and treated appropriately during the statistical analysis. Additional confounding factors such as variability in pain and narcotic usage will be discussed in the manuscript. Investigators do not anticipate potential confounders will significantly affect the results of the study.

Standard of Care Procedures

All participants will receive injection with BoNT (Botox, Allergan) as standard clinical care. OAB participants will receive 100 units and NDO participants will receive 200 units per FDA guidelines. All participants will also undergo standard recommended preoperative analgesia per manufacture guidelines, intravesical instillation of 2% lidocaine (60ml) + sodium bicarbonate (10ml), administered 40 minutes prior to cystoscopic bladder injection. Viscous lidocaine will be used to anesthetize the urethra.

BoNT will be prepared and injected per manufacturer guidelines. After reconstitution in 10ml of normal saline, BoNT is injection in 0.5ml increments (20 injections total) into the detrusor muscle layer of the bladder dome in a standardized square pattern (Figure 1). Injection pattern will also not differ from clinical standard practice, and all patients receive the same, trigone sparing injection pattern [32].

Figure 1. Bladder injection pattern.

Regardless of participation, patients will undergo the injection procedure with BoNT, and will receive the analgesia per standard of care, both of which will be billed to the patient's insurance company. Costs associated with the BoNT therapy, including the in-office procedure visit, follow-up visit, physician fees, bladder testing conducted during two weeks follow-up, and any additional follow-up care, will be billed to the patient's insurance company, or will be the responsibility of the patient.

Information regarding volume of BoNT used in the procedure, as well as analgesia information will be collected for research purposes. Voiding trial samples, if clean, will be discarded as standard office procedures. If an infection is present, the sample is sent to the lab as standard office procedures required for appropriate medical management.

Research Intervention

Participants randomized to the active group will receive a rectal belladonna & opiate (B&O) suppository along with standard analgesia 40 minutes prior to bladder injection.

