Participants randomized to placebo will also receive standard analgesia as well as a rectal suppository composed of inactive base 40 minutes prior to bladder injection.

Study drug will be provided by a compounding pharmacy [REDACTED] that can produce visibly identical active and placebo suppositories. Dosage of the compounded active suppository is belladonna 16.2mg and morphine 7.5mg, which matches the commercially available belladonna and opium suppositories (belladonna 16.2mg + opium powder 60mg). Compounded belladonna dose will be the same (16.2mg) and morphine equivalent dose (7.5mg) will be used in place of powdered opium component. Using morphine, which carries a Schedule 2 narcotics classification, requires adhering to DEA restrictions for compounding purposes. The Principal Investigator will write an authentic prescription for each participant enrolled in the study (each prescription will refer to the research study, and will request "B&O suppository or placebo"), which will assist with adhering to guidelines for using Schedule 2 narcotics in clinical practice. Blinding afforded by using similar suppositories also enhances study rigor.

The B&O suppository and placebo pills participants receive will not be billed to the patient's insurance company.

Origin, Tracking, and Dispensing of Suppositories

The placebos and B&O suppositories will be purchased from [REDACTED]

The pharmacy will compound belladonna and morphine suppositories (16.2mg/7.5mg) to the same dose equivalent of opium (60 mg). Compounding the belladonna and morphine (morphine sulfate 7.5 mg is approximately equivalent to powdered opium 60 mg) would be more feasible for the study than using commercial B&O suppositories because the pharmacy cannot duplicate the exact size and shape of the commercially available B&O suppositories for research purposes. Due to the research being double-blinded to the participant and the investigators, compounded belladonna and morphine suppositories will be used. Compounded belladonna and morphine is a commonly used, and is pharmacologically equivalent to belladonna and opium suppositories.

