A sample from each batch of compounded suppositories will be sent off for third-party testing to test the suppositories for chemical validity.

Participant Timeline

The length of participation in this study will be approximately two weeks from the day of the injection procedure. Table 2 illustrates the procedures or tasks to be completed during each appointment.

Table 2. ROBIN Trial Participant Timeline	
Appointment	Task/Objective
Patient Consents to Undergo Bladder Injection Therapy	
 • Patient elects to receive BoNT therapy as standard of care treatment for overactive bladder, neurogenic detrusor overactivity, or refractory interstitial cystitis • If patient meets inclusion criteria, patient is consented and offered enrollment into the study • Participant receives a participant ID number based on sequential numbering • Principal Investigator completes prescription and sends to compounding pharmacy to fill based on participant ID number
Day Prior to Procedure	
 • If informed consent is obtained, the blinded suppository will be hand delivered to the clinic by the compounding pharmacy • The suppository will be locked in a medicinal refrigerator until time of the procedure
Day of Procedure	
 • Participant checks in for procedure, and completes pain assessment (P_0) • Principal Investigator administers the suppository or placebo to the participant • Participant completes pain assessment after receiving analgesia for the procedure (P_a) • Participant undergoes BoNT procedure and completes pain assessment (P_{10}, P_{20}) • Participant completes voiding residual trial • Adverse effects or serious events are assessed • Participant is released from clinic
2-weeks follow-up visit	
 • Participant completes voiding residual trial and adverse effects or serious events are assessed • Participant receives \$25 gift card incentive for completing the study

Risks to Subjects

Because the patient has already given consent to receive the BoNT therapy, any risks associated with the procedure while participating in this study are within normal bounds for any patient electing to undergo the procedure. Overall, the risks involving the use of the B&O suppository are comparable to not utilizing it during the BoNT therapy

procedure. Use of this particular suppository should not significantly increase or decrease risks to the patient.

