However, investigators believe that there are risks associated with this study. Physical risks associated with participating in this study, and related to study procedures include drowsiness/nausea associated with the B&O suppository if the participant is randomized to the active group. As standard of care after the BoNT procedure, patients are required to have a driver, and are advised on to operative a moving vehicle. Participants receiving the placebo may experience discomfort with the procedure, which the patient is aware of during the consent process for the BoNT therapy.

This research study involves exposure to pain and discomfort, however the risk is associated with routine clinical care since there are no established guidelines or recommendations for suppository use with analgesia during the BoNT therapy. The risk of discomfort and drowsiness/nausea associated with the study is minimal, and if the patient were to not participate in the study, would typically receive the B&O suppository as part of the Principal Investigator's routine standard of care. Researchers believe there is less than minimal risk associated with psychological, economic, social, and legal aspects of this study.

Loss of anonymity is a risk associated with research projects that involve human subjects. The research staff working on this study will take every precaution to guard patient identity in accordance with HIPPA standards. All study information and data will be grouped in aggregate and no individual information will be reported. No patient will be identified by name and protections will be in place to keep individual information confidential and anonymous.

However, risks are reasonable to the potential benefit from the study. Participation in this study will contribute to a better understanding of the treatment of bladder injection pain, which outweighs the minimal risk associated with the active group intervention. Additionally, this study may also help other patients that need to have the BoNT therapy in the future, have a better understanding of treatment options for overactive bladder, neurogenic detrusor overactivity, and refractory interstitial cystitis. Furthermore, information collected from this study would provide clinicians methods that could potentially reduce patient pain during in-office procedures, and would reduce potential healthcare costs associated with performing this type of procedure in a hospital facility.

Study Sites

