Aside from suppository placement, BoNT injection protocols that are in compliance with best practices established by Allergan® and the FDA will be followed. In summary, BoNT will be reconstituted in 10ml normal saline and injected in 1/2ml increments (20 injections). Standard analgesia consists of bladder instillation with 50-60ml of 1% lidocaine solution with 10ml of sodium bicarbonate. Instillation is maintained for 40 minutes prior to the procedure. During that time, the patient will rotate while on procedure table (10 minutes on supine, 10 minutes prone, 10 on each side) to maximize bladder wall contact with anesthetic. The patient will then be placed in lithotomy position for cystoscopic injection of BoNT. A 17 french 30 degree cystoscope will be used. Injection will be carried out using a flexible botox injection needle designed for the procedure. All patients will undergo standard screening for preoperative UTI and antibiotic prophylaxis per accepted guidelines.

After 40 minutes of receiving the analgesic and suppository, and right before the procedure, the participant will be asked to report their bladder pain using a numeric rating scale (Appendix D – Pain Assessment Form – Pa-P20).

Patients will undergo 20 total injections at time of BoNT treatment. An investigator will perform pain assessments during the procedure. During the procedure, the participant will be asked their bladder pain using the numeric rating scale after the first 10 of 20 injections performed during the procedure and after the next 10 of 20 performed during the procedure (Appendix D – Pain Assessment Form – Pa-P20).

After the procedure is completed, the participant will be asked to complete a voiding trial, and will be given a pain assessment form, answering a Likert scale question regarding their satisfaction with their pain management during the procedure (Appendix E – Pain Assessment Form - Post BoNT). After the voiding trial is completed and the Principal Investigator has provided standard medical counseling and care after the procedure, the participant is released from the clinic.

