In the case an adverse event were to occur, the study investigator(s) will assume responsibility for reporting and documenting any complications. All serious events and adverse effects will be recorded on the participant's case record forms. In addition, all serious adverse and unanticipated adverse effects will be reported to the Institutional Review Boards by telephone, or in writing, within five (5) business days after the investigators first learn of the event by either the investigator(s) or the project coordinator.

The investigators are required to document all general medical complications, including, but not limited to the following: date of occurrence, date diagnosed, type of complication, and treatment. The investigator(s) and research assistant are responsible for complying with any reporting requirement of the reviewing IRBs.

Adverse events will be assessed after the suppository has been used, during the procedure, and during the voiding trial. During the two week follow-up visit, adverse events will also be assessed. The investigators do not believe there will be a need to stop or alter the study, but will stop the study if requested by the Institutional Review Board.

Record Retention

All study related documents (research materials such as protocols, IRB documents, participant information and data forms after completion of data collection and analysis) will be retained for fifteen (15) years from the date of initial IRB approval, and will be kept in locked cabinets located at the University of Kansas School of Medicine – Wichita Department of Obstetrics and Gynecology, [REDACTED]

[REDACTED]. At the time of document

disposal, documents will be shredded according to KUMC Research Institute Record Retention guidelines.

Dissemination of Results

Once the research is completed, it will be submitted to gynecologic journals and conferences, particularly those specializing in urogynecology.

Project Timeline

The project seeks to obtain Institutional Review Board approval from the IRBs by September 2015 (Table 5). This research project is anticipated to be completed by April 2017. The investigators anticipate conducting preliminary analysis after one year, and will complete continuing review forms as needed to complete the study.

Table 5. ROBIN Trial Project Timeline													
PROJECT LAUNCH Project Deliverables (X)	Academic Year 2015 - 2016												
	7	8	9	10	11	12	1	2	3	4	5	6	7
	J	A	S	O	N	D	J	F	M	A	M	J	J

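### After clinic release, reactions to the randomised suppository are picked up only by recall at the 2-week visit or by spontaneous report, so mild short-lived effects are likely to be under-reported

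*Combined protocol and SAP*

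**What the plan says.** Adverse Event Assessment and Reporting sets the safety contacts. On the procedure day: "Adverse events will be assessed after the suppository has been used, during the procedure, and during the voiding trial". After that: "During the two week follow-up visit, adverse events will also be assessed". The same section requires all adverse effects to go on the case record form, and complications to be documented with the date they occurred.

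Table 2 (Participant Timeline) agrees. Events are assessed on the procedure day before release, and the 2-week row reads: "Participant completes voiding residual trial and adverse effects or serious events are assessed". Data Collection Procedures says that once the voiding trial and counselling are done, "the participant is released from the clinic". It gives no minimum stay.

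The section Research Intervention gives the timing of the exposure: "Participants randomized to the active group will receive a rectal belladonna & opiate (B&O) suppository along with standard analgesia 40 minutes prior to bladder injection".

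Background lists the suppository's possible reactions, at undefined frequency. They include dizziness, drowsiness, nausea or vomiting, constipation, dry mouth, urinary retention and visual effects. Risks to Subjects names drowsiness and nausea as the physical risk in the active arm, and in that paragraph notes that "patients are required to have a driver" as standard care after the procedure.

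**The concern.** Botulinum toxin and lidocaine are given to everyone. The suppository is all that differs between the arms, so the arms can be compared on its tolerability. The contacts cover the clinic stay and day 14, but no prompt or record is scheduled for the hours after release, when drowsiness, dizziness or nausea from a dose given shortly before could still be present.

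A participant who felt drowsy or sick that evening has to remember it two weeks later and think it worth mentioning. Mild events that have resolved are the ones least likely to survive that delay. Since these reactions belong to the active product, the loss would fall mainly in the active arm. At stake is the usefulness of the trial's tolerability description for a product that, according to Risks to Subjects and Alternatives to Participation, the investigator already uses routinely.

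**Working it through.** **1. The plan's own figure.** The documents give no figure for adverse event coverage. The only calculated quantity is the sample size. With means of 4.5 and 8 (difference 3.5), SD 3, two-sided 0.05 and power 0.8, the two-sample t-test solution is 12.57, rounded up to the stated 13 per group. Nothing in this point changes it.

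**2. Sequence of safety contacts.**

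| Time | Adverse event assessment | Source |
|---|---|---|
| Suppository given, 40 minutes before injection | Yes, after use | Research Intervention; Adverse Event Assessment and Reporting |
| Procedure | Yes | Adverse Event Assessment and Reporting |
| Voiding trial | Yes | Adverse Event Assessment and Reporting |
| Release to 2-week visit | None scheduled | Table 2; Data Collection Procedures |
| 2-week visit | Yes, looking back | Table 2; Adverse Event Assessment and Reporting |

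**3. Can the unobserved share be calculated?** It needs two inputs that the protocol does not state.

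- Clinic time after dosing: only the 40 minutes before injection is given.
- Duration of action: Background says only that one dose wears off long before the toxin's 2-4 week onset period is complete.

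The nearest figure is the dosing frequency of the commercial product, which "may be dosed as 1 suppository 1-4 times a day". Origin, Tracking, and Dispensing of Suppositories says the compounded product "is pharmacologically equivalent to belladonna and opium suppositories", so the frequency can be carried over. A dosing frequency is still not a duration of action. What follows is an illustration under stated assumptions.

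Spacing implied by frequency: 24/4 = 6 h to 24/1 = 24 h.

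Share after release = 1 - (stay after dosing / assumed duration).

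| Assumed stay after dosing | Assumed duration 6 h | Assumed duration 24 h |
|---|---|---|
| 40 min | 1 - 40/360 = 88.9% | 1 - 40/1440 = 97.2% |
| 2 h | 1 - 2/6 = 66.7% | 1 - 2/24 = 91.7% |
| 3 h | 1 - 3/6 = 50.0% | 1 - 3/24 = 87.5% |

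If effects last 6 h, most of that time falls after release unless the stay reaches 3 h. The 24 h column is weak, since permitting once-daily use does not show a day of action. The table gives shares of time, not shares of events.

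**4. Weight of one event.** With 13 active participants, one participant whose reaction is missed changes the observed proportion by 1/13 = 7.7 percentage points. This shows how coarse the safety data are. It does not estimate how many events would be missed.

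**The case against.** The strongest reply is that events after release are not lost by design. Adverse events are assessed at 2 weeks, all adverse effects must go on the form, and complications carry a date, so a first-evening event can be recorded and placed in time. Research-Related Injury also tells participants to contact the investigator at once if a study procedure injures them. This stands. A reader might infer that the post-release hours go unrecorded, and the documents do not support that. They are not recorded in real time.

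A reader might also take the shares above as the fraction of the drug's action that is missed. That is not supported either, because both the stay and the duration are assumed. The suppository is also timed to be working by the injection, so the onset of its effects is likely to fall inside the observed window. Background adds that systemic effect by this route is minimal.

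A third inference would be that the schedule biases the trial towards finding no added harm. The plan specifies no comparative harm analysis. The statement in Risks to Subjects that risks are comparable is a prior statement, soon followed by an acknowledgement of drowsiness and nausea. Under-reporting would weaken a description of tolerability, but there is no planned harm test for it to distort.

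Urinary retention is better covered than the other reactions, through the voiding trial before release and the 2-week residual. The content of the 2-week form (Appendix F) is not in the text reviewed, so whether it prompts for the first day cannot be judged.

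None of this provides same-day recording of drowsiness, dizziness or nausea after release.

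**Conclusion.** The point holds in a limited form. Between release and the 2-week visit no adverse event ascertainment is scheduled, so suppository reactions in that period depend on recall or spontaneous report. Mild transient reactions are likely to be under-reported, mainly in the active arm. That is a judgement about recall and about which arm has the reactions. The documents contain no data on it, and the size of the loss cannot be given as a firm percentage.

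The conclusion rests on there being no call, diary or next-day contact in the text reviewed, and on some effects outlasting the clinic stay. The primary analysis and sample size are unaffected. This is an inexpensive improvement to the safety data of a 26-person pilot.

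**What to change.** Add to Adverse Event Assessment and Reporting, and to the procedure-day and 2-week rows of Table 2, a one-page symptom card given at release and identical in both arms so that blinding is kept. It should list the reactions named in Background, each with yes/no, start time and severity, for the rest of the procedure day and the next day, with an instruction to fill it in at the time. Collect it at the existing 2-week visit. If it is not returned, ask specifically about the first day and mark those answers as recalled. Report events in the first 24 hours by arm, descriptively and without a test.

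The cost is one printed form (the budget already has a line for paper and printing), a short protocol addition and IRB approval. No extra visit, staff or procedure is needed. The downside is a small burden on participants, and some cards will be unreturned or filled in late from memory.
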